1. PROTOCOL SUMMARY

1.1 Schedule of Activities (SoA)

Table 1: Schedule of Activities (SoA)

Study Phase	Screening Phase	Treatment Phase ^a		Follow-up Phase
Cycle		Cycles 1-6	EOT	EOS
Visit No.	1	2-7 (Day 1 of each cycle)	8	
Study Days	-6 to 0	1-168 (28 days per cycle)	170	28 days post-EOT
Screening/Enrolment visit				
Informed consent ^s	X			
Eligibility Criteria	X			
Demographics/ Review medical history	X			
ECOG Performance Status	X	X	X	
General Physical examination ^b	X	Symptom-directed physical examination only		
Concomitant medication recording	Continuous from the time of ICF until 28 days after the last Acalabrutinib dose in the treatment phase.			
Study Drug Administration				
Acalabrutinib dosing		The recommended dose is Acalabrutinib 100 mg capsules BID, starting on Day 1 Cycle 1, until disease progression or unacceptable toxicity. Each cycle of treatment is 28 days.		
Disease Evaluations (Disease characteristics will be performed as per routine clinical practice)				
Baseline Disease Characteristics	X			
Safety Evaluations (baseline and each treatment visit) [*]				
Physical examination ^b	X	Symptom-directed physical examination only		
Vital parameters ^c	X	X	X	
Adverse event monitoring	Continuous from the time of ICF until 28 days after last study dose of Acalabrutinib.			

Study Phase	Screening Phase	Treatment Phase ^a		Follow-up Phase
Cycle		Cycles 1-6	EOT	EOS
Visit No.	1	2-7 (Day 1 of each cycle)	8	
Study Days	-6 to 0	1-168 (28 days per cycle)	170	28 days post-EOT
12-lead ECG	X	X	X	
Lymph node biopsy ^d	X			
Next-generation sequencing (NGS)-CLL panel ^e	X			
Haematology ^f & Biochemistry ^g	X	X	X	
Urinalysis ^h	X	X	X	
Pregnancy Test ⁱ	X	X	X	
Chest X-ray ^j	X	X	X	
Efficacy Evaluations (once in 3 months)				
CT/MRI ^k	X	X	X	
EORTC QLQ-C30 Questionnaire	X	X	X	
[§] Patients must sign the informed consent form before any study-specific procedures are performed. [*] Procedures conducted as part of the patient's routine clinical management (e.g., blood count) and obtained before signing of the Informed Consent Form (ICF) may be utilised for screening or baseline purposes provided the procedures meet the protocol-specified criteria and were performed within the time frame (-6 to 0 day) ^a Treatment phase from Day 1 to Day 168. The treatment with Acalabrutinib will be continued until disease progression or unacceptable drug-related toxicity, whichever occurs earlier. ^b The screening physical examination will include, at a minimum, the general appearance of the subject, height (screening only) and weight, and examination of the skin, eyes, ears, nose, throat, lungs, heart, abdomen, extremities, musculoskeletal system, lymphatic system, and nervous system. Symptom-directed physical examination, including tumour assessments by palpation, are done thereafter. ^c Vital signs (blood pressure, heart rate, and temperature) will be assessed after the patient has rested in the sitting position. ^d Lymph node biopsy will be conducted in patients with lymphadenopathy. However, a report of previous lymph node biopsy performed within 06 months before the study enrolment could be considered if the patient did not receive any medication during that period				

Study Phase	Screening Phase	Treatment Phase ^a		Follow-up Phase
Cycle		Cycles 1-6	EOT	EOS
Visit No.	1	2-7 (Day 1 of each cycle)	8	
Study Days	-6 to 0	1-168 (28 days per cycle)	170	28 days post-EOT

^e Next-generation sequencing will be conducted to understand the genetic profile in Indian settings. Molecular cytogenetics (FISH) for del(13q), del(11q), del(17p), trisomy 12 in peripheral blood lymphocytes; TP53 mutation; immunoglobulin variable heavy chain (IGHV) mutational status will be assessed before the start of treatment in CLL/SLL-naïve patients, or CLL/SLL patients who did not have their report. However, MCL patients are Relapsed/Refractory and their previous report data will be used. A six months old report can be considered for both the conditions.

^f Haematology will include a complete blood cell count [white blood cell count, haemoglobin (Hb), haematocrit, reticulocyte, and platelet count] and differential leukocyte count, including both percent and an absolute number of lymphocytes. Haematology need not be repeated on Cycle 1 Day 1 if screening haematology was within 5 days

^g Biochemistry will include albumin, Total bilirubin, Total protein, Alkaline Phosphatase (ALP), Alanine Aminotransferase (ALT, SGPT), Aspartate Aminotransferase (AST, SGOT), Gamma-glutamyl transferase (GGT), Lactate Dehydrogenase (LDH), Lipase, Amylase, Blood Glucose, Magnesium, Potassium, Bicarbonate, Sodium, Calcium, Chloride, Creatinine (creatinine clearance), Urea or Blood Urea Nitrogen (BUN), Haptoglobin, b2-microglobulin. Serum biochemistry need not be repeated on Cycle 1 Day 1 if screening chemistry was within 5 days.

^h Urinalysis: pH, ketones, specific gravity, bilirubin, protein, blood, and glucose.

ⁱ A urine pregnancy test will be conducted in all females of child bearing potential at the time of screening and during the study (treatment phase)

^j Chest X-ray will be done as a symptom directed investigation. Patients with signs and symptoms of Pneumonia will be allowed to go for chest X-ray investigation.

^k CT or MRI scans will be performed prior to the first study medication administration (dosing). CT or MRI scans are applicable for the patients with lymphadenopathy or organomegaly. Patients with abnormalities of blood parameters without any lymphadenopathy or organomegaly will not undergo CT or MRI scans. Patients who will be undergoing CT, should have baseline and every 3-months reports

Note: CMV, HIV, and Hepatitis serology testing will be conducted at the screening.

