1.2 Synopsis

Protocol Title: A prospective, multi-centre, phase IV clinical trial to assess the safety and efficacy of Acalabrutinib capsules in Indian adult patients with chronic lymphocytic leukaemia and relapsed and refractory mantle cell lymphoma

Version: 1.0 Date: 01 Sep 2020

Study sites and number of patients planned

No. of total screened patients: Approximately 150

No. of total enrolled patients: Approximately 100

No. of study sites: 10

Total planned study period	
Estimated date of the first patient in	Q4 2020
Estimated date of the last patient in	Q2 2021
Estimated date of last patient last visit	Q4 2021
Estimated date of database lock	Q2 2022
Clinical study report	Q3 2022

Rationale

Chronic lymphocytic leukaemia (CLL) is a malignancy of B cells that predominantly affects an elderly population. It is the most prevalent form of adult leukaemia, with an age-adjusted incidence of 3.3–6.4 per 100,000 person-years and a median age at diagnosis of 70 years (Noone AM, April 2018). The diagnosis of CLL is established using peripheral blood and immunophenotyping and requires the presence of a minimum of $5 \times 10^9/L$ monoclonal B cells that co-express the surface antigens CD5, CD19, CD20, and CD23. In routine practice, patients with asymptomatic early-stage disease should be monitored without therapy unless they have evidence of disease progression or disease-related symptoms. Treatment of CLL is initiated once there is evidence of progressive or symptomatic/active disease as defined by iwCLL guidelines (Hallek et al., 2018; Hallek et al., 2008). Despite the relatively long life expectancy for early-stage disease, CLL remains an incurable disease.

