5.1 Inclusion criteria

Patients are eligible to be included in the study only if all of the following inclusion criteria and none of the exclusion criteria apply:

1. Men and Women aged 18 yrs or more.
2. Eastern Cooperative Oncology Group (ECOG) performance status of 0,1, or 2
3. Able to receive all outpatient treatments, all laboratory monitoring, and all radiologic evaluations.
4. The following laboratory parameters:
 - a. Absolute neutrophil count (ANC) ≥ 750 cells/ μL or ≥ 500 cells/ μL in patients with documented bone marrow involvement, and independent of growth factor support 07 days before the assessment
 - b. Platelet count $\geq 50,000$ cells/ μL or $\geq 30,000$ cells/ μL in patients with documented bone marrow involvement, and without transfusion support 07 days before the assessment
 - c. Aspartate transaminase (AST) and Alanine transaminase (ALT) ≤ 2.0 x ULN

- d. Total bilirubin $\leq 1.5 \times$ ULN
 - e. Estimated creatinine clearance of ≥ 30 mL/min
5. Refractory disease defined as achieving less than partial response with the most recent treatment before study entry
 6. Provision of signed, written and dated informed consent prior to any study-specific procedures
 7. The patients of either CLL or MCL:
 - a. **CLL patients:**
 - i. Treatment naïve or ≥ 1 prior systemic therapy for CLL
 - ii. Diagnosis of CD20+ CLL that meets published diagnostic criteria (Hallek et al. 2018)
 - iii. An active disease that meets ≥ 1 of the following iwCLL 2018 criteria for requiring treatment
 - 1) Evidence of progressive marrow failure as manifested by the development of, or worsening of, anaemia and/or thrombocytopenia. Cut-off levels of Hb < 10 g/dL or platelet counts $< 100 \times 10^9/L$ are generally regarded as an indication for treatment. However, in some patients, platelet counts $< 100 \times 10^9/L$ may remain stable over a long period; this situation does not automatically require therapeutic intervention.
 - 2) Massive (i.e., ≥ 6 cm below the left costal margin) or progressive or symptomatic splenomegaly.
 - 3) Massive nodes (i.e., ≥ 10 cm in longest diameter) or progressive or symptomatic lymphadenopathy.

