8. STUDY ASSESSMENTS AND PROCEDURES

Study procedures and their timing are summarised in the SoA, Table 1.

Written informed consent for participation in the study must be obtained before performing any study specific screening tests or evaluations. Informed Consent Forms for enrolled patients and for patients who are not subsequently enrolled will be maintained at the study site.

Documented evidence of CLL/SLL and MCL positive status from previous testing is acceptable, otherwise it has to be assessed at a local laboratory that is experienced/certified in CLL/SLL and MCL testing using an accurate and validated assay.

Women with child bearing potential and male patients with partners of child bearing potential who are sexually active will have to agree to use a highly effective, non-hormonal form of contraception (such as surgical sterilization) or two effective forms of non-hormonal contraception (such as a barrier method of contraception in conjunction with spermicidal jelly) during and for at least 6-months post-study treatment.

Screening tests and evaluations will be performed within 7 days prior to the first study medication administration (dosing). CT or MRI scans will be performed prior to the first study medication administration (dosing). CT or MRI scans are applicable for the patients with lymphadenopathy or organomegaly. Patients with abnormalities of blood parameters without any lymphadenopathy or organomegaly will not undergo CT or MRI scans. Patients who will be undergoing CT, should have baseline and every 3-months reports.

All screening evaluations must be completed and reviewed to confirm that patients meet all eligibility criteria before enrolment. The investigator will maintain a screening log to record details of all patients screened and to confirm eligibility or record reasons for screening failure, as applicable.

The safety assessments during the treatment visit will be performed at the start of each treatment cycle. However, efficacy assessments will be scheduled every three months during the study treatment period and EOT.

The Investigator will ensure that data are recorded in the eCRF.

The Investigator ensures the accuracy, completeness for eCRFs that includes: timeliness of the data recorded and query resolution according to the Clinical Study Agreement. The Investigator will sign the completed eCRFs.

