- Treatment phase from Day 1 to Day 168. The treatment with Acalabrutinib will be continued until disease progression or unacceptable drug-related toxicity, whichever occurs earlier.
- The screening physical examination will include, at a minimum, the general appearance of the Patient, height (screening only) and weight, and examination of the skin, eyes, ears, nose, throat, lungs, heart, abdomen, extremities, musculoskeletal system, lymphatic system, and nervous system. Symptom-directed physical examination, including tumour assessments by palpation, are done thereafter.
- Vital signs (blood pressure, heart rate, and temperature) will be assessed after the Patient has rested in the sitting position.

Document Title:	Document ID:	BP04-01
Statistical Analysis Plan	Version Number:	3.1
	Effective Date:	25-Nov-2021

- d. Lymph node biopsy will be conducted in Patients with lymphadenopathy. However, a report of previous lymph node biopsy performed within 06 months before the study enrolment could be considered if the Patient did not receive any medication during that period

Study Phase	Screening Phase	Treatment Phase a		Follow-up Phase
Cycle		Cycles 1-6	EOT	EOS
Visit No.	1	2-7 (Day 1 of each cycle)	8	
Study Days	-6 to 0	1-168 (28 days per cycle)	170	28 days post-EOT

- e. Next-generation sequencing will be conducted to understand the genetic profile in Indian settings. Molecular cytogenetics (FISH) for del(13q), del(11q), del(17p), trisomy 12 in peripheral blood lymphocytes; TP53 mutation; immunoglobulin variable heavy chain (IGHV) mutational status will be assessed before the start of treatment in CLL/SLL-naïve Patients, or CLL/SLL Patients who did not have their report. However, MCL Patients are Relapsed/Refractory and their previous report data will be used. A six months old report can be considered for both the conditions.
- f. Haematology will include a complete blood cell count [white blood cell count, haemoglobin (Hb), haematocrit, reticulocyte, and platelet count] and differential leukocyte count, including both percent and an absolute number of lymphocytes. Haematology need not be repeated on Cycle 1 Day 1 if screening haematology was within 5 days.

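### Footnote d makes a screening node biopsy the default even in blood-confirmed CLL, where no stated item uses the result; separately, pre-dose adverse events enter the main safety table

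*Protocol*

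**What the plan says.** **Biopsy.** The Schedule of Activities (Protocol 1.1) puts lymph node biopsy at screening, Day -6 to 0, among the safety evaluations. Footnote d reads "Lymph node biopsy will be conducted in patients with lymphadenopathy". The only alternative is that "a report of previous lymph node biopsy performed within 06 months before the study enrolment could be considered", on condition that the patient had no medication in the interval. SAP 2.2.5 repeats the instruction: "Lymph node biopsy will be conducted in Patients with lymphadenopathy". Neither document limits it by disease or diagnostic need, or says what the result is for. Elsewhere, Protocol 1.2 states "The diagnosis of CLL is established using peripheral blood and immunophenotyping", and Protocol Section 8 states "Documented evidence of CLL/SLL and MCL positive status from previous testing is acceptable", with no age limit on that evidence.

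**Adverse events.** Protocol 8.2.2 collects events from the signing of consent, and Appendix B 1 counts an event as an AE even when no study drug has yet been given. SAP Table 14.3.1 is built on the Full Analysis Set (dosed patients) and counts patients with any AE. Its grade, causality, action, withdrawal, treatment and outcome rows take patients with any AE as their denominator. The SAP does not define a treatment-emergent event.

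**The concern.** These are two separate matters.

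First, a patient with CLL documented on blood, enlarged nodes and no qualifying recent biopsy report falls under footnote d, even though Section 8 accepts the existing evidence of disease. The biopsy comes within days of starting a drug for which bleeding is an event of special interest. Inclusion criterion 4b admits platelets down to 30,000/µL "in patients with documented bone marrow involvement, and without transfusion support 07 days before the assessment", and open surgical biopsy is one of the methods in SAP Table 14.1.6. A patient who then fails screening may have been biopsied and never receive the drug.

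Second, a patient whose only event precedes the first dose counts towards incidence in the primary safety table. That patient also joins the denominator of the causality row without being able to contribute a drug-related event. Protocol 4.2 cites treatment-emergent events from a pooled safety analysis of 1,040 patients, so a comparison with it would be on a different basis. This problem would remain if footnote d were deleted.

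**Working it through.** **Part 1: does any stated item use the biopsy result in CLL confirmed on blood?** No formula applies, so the possible uses are set side by side.

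| Possible use | What the plan specifies | Node tissue used? |
|---|---|---|
| Diagnosis | Peripheral blood and immunophenotyping (Protocol 1.2) | No |
| Eligibility | CD20+ CLL by published criteria, plus active disease on clinical and laboratory criteria (5.1, item 7a) | No |
| Cytogenetics | FISH, including "trisomy 12 in peripheral blood lymphocytes" (1.1, footnote e) | No |
| Response | Node size by CT and examination, organ size, symptoms, blood counts (8.1.1, Table 4) | No |
| Reporting | Node enlargement and size, whether a biopsy was done within six months, method (SAP Table 14.1.6); Listing 16.2.4 adds dates, interval medication and a yes/no field on need | No pathology result |

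Footnote e gives a purpose for sequencing, and footnotes j and k tie chest X-ray and CT/MRI to a clinical finding and its relevance. Footnote d gives no purpose. It names lymphadenopathy only.

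Number affected: the documents give neither the share of CLL/SLL patients with lymphadenopathy nor the share with a qualifying report. The bound is 0 to 90 of the planned cohort. For screen failures, the synopsis gives "No. of total screened patients: Approximately 150" and about 100 enrolled, so about 150 − 100 = 50 are screened but not enrolled. Their split by disease is not given.

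**Part 2: effect of pre-dose events on Table 14.3.1.** The cohort sizes of 90 and 10 come from Protocol 4.1. No event rates are given, so the following are assumed: p, the probability of an event on or after the first dose, 60% to 95%; q, the probability of a pre-dose event, 2% to 10%; the two independent.

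- Rise in any-AE incidence = (p + q − pq) − p = q(1 − p).
- Low end: 0.02 × (1 − 0.95) = 0.001, or 0.1 points.
- Middle: 0.05 × (1 − 0.80) = 0.010, or 1.0 point.
- High end: 0.10 × (1 − 0.60) = 0.040, or 4.0 points.
- One patient with only a pre-dose event: 1/90 = 1.1 points in CLL/SLL; 1/10 = 10 points in MCL.

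Causality row at n = 90, p = 80%, q = 10%: 0.80 × 90 = 72 patients have an on-treatment event and 18 do not. Pre-dose-only patients are 0.10 × 18 = 1.8 in expectation. With an assumed 36 related, 36/72 = 50.0% becomes 36/73.8 = 48.8%.

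**The case against.** **On the biopsy.** Mock tables are not the case report form, so a missing result column does not show that pathology goes unread. Listing 16.2.4 records whether a node is enlarged separately from whether a biopsy was needed, which suggests that sites may answer no. It also narrows the interval medication to that given for the study indication, which is looser than footnote d. Tissue has a real role in SLL and MCL. The bleeding risk is reduced because bleeding diathesis and anticoagulation in the previous seven days are excluded, and fine-needle aspiration is a listed method. All of this stands. It does not supply a rule for sparing a blood-confirmed CLL patient, because footnote d remains the only instruction.

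A reader might infer a count. Applying the 90:10 split to screening gives 150 × 0.90 = 135 CLL/SLL patients, and a guessed 10% to 50% biopsy rate gives 14 to 68. The documents support neither the split nor the rate, and a site could complete blood tests before any biopsy.

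A reader might also think the footnote should keep biopsy for suspected transformation. Exclusion 1 already bars currently suspected Richter's syndrome and Protocol 5.4 bars rescreening, so that would direct an invasive procedure at patients who cannot enter.

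**On adverse events.** Counting from consent agrees with Appendix B 1. Appendix B 7 asks whether the drug had been received, so pre-dose events should not be rated related. Causality to study procedures is recorded for SAEs, and start dates are listed. These points protect the numerator and make events traceable. They do not remove pre-dose events from the incidence or from the denominators.

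**Conclusion.** Both points hold, at modest weight. Footnote d makes biopsy the default in lymphadenopathy, and for CLL confirmed on blood no stated item depends on the result. This is a matter of patient burden and wording. It changes no response criterion or sample size. Its scale is unknown within the bound shown above.

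The adverse-event point concerns the primary output, but its expected effect is small and rests wholly on the assumed p and q and on independence. Its main practical weight is in the MCL column. A reader might infer a larger dilution of the causality row, for example 36/76 = 47.4%. That needs four pre-dose-only patients, which with 72 of 90 having on-treatment events means q = 4/18 = 22%, well outside the assumed range. Nor do the documents show that biopsy complications would account for the pre-dose events: the calculation covers any event between consent and first dose.

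**What to change.** **Footnote d in Protocol 1.1, and its copy in SAP 2.2.5.** Replace with:

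> Lymph node biopsy is done only where tissue is needed to establish the diagnosis (SLL without a histology report, or MCL without a report of t(11;14) or cyclin D1). It is not required in CLL confirmed on peripheral blood. An earlier diagnostic report is acceptable.

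The last sentence brings the footnote into line with Section 8. The cost is a protocol amendment with IRB/IEC approval across the 10 planned sites, and less node histology at baseline. If enrolment has closed, this change is moot.

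**SAP Table 14.3.1.** Base the main counts, and the denominators of the rows that now use patients with any AE, on events with onset on or after the first dose. Show pre-dose events in a separate row. The cost is one date rule and one row. The onset dates and times are already collected (Protocol 8.2.4; SAP Listing 16.2.11.1), so no new data are needed and the change does not depend on enrolment status.

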1.2 Synopsis

Protocol Title: A prospective, multi-centre, phase IV clinical trial to assess the safety and efficacy of Acalabrutinib capsules in Indian adult patients with chronic lymphocytic leukaemia and relapsed and refractory mantle cell lymphoma

Version: 1.0 Date: 01 Sep 2020

Study sites and number of patients planned

No. of total screened patients: Approximately 150

No. of total enrolled patients: Approximately 100

No. of study sites: 10

Total planned study period	
Estimated date of the first patient in	Q4 2020
Estimated date of the last patient in	Q2 2021
Estimated date of last patient last visit	Q4 2021
Estimated date of database lock	Q2 2022
Clinical study report	Q3 2022

Rationale

Chronic lymphocytic leukaemia (CLL) is a malignancy of B cells that predominantly affects an elderly population. It is the most prevalent form of adult leukaemia, with an age-adjusted incidence of 3.3–6.4 per 100,000 person-years and a median age at diagnosis of 70 years (Noone AM, April 2018). The diagnosis of CLL is established using peripheral blood and immunophenotyping and requires the presence of a minimum of $5 \times 10^9/L$ monoclonal B cells that co-express the surface antigens CD5, CD19, CD20, and CD23. In routine practice, patients with asymptomatic early-stage disease should be monitored without therapy unless they have evidence of disease progression or disease-related symptoms. Treatment of CLL is initiated once there is evidence of progressive or symptomatic/active disease as defined by iwCLL guidelines (Hallek et al., 2018; Hallek et al., 2008). Despite the relatively long life expectancy for early-stage disease, CLL remains an incurable disease.

The incidence of CLL in India is 0.41 per 100,000 person-years; not as common as in the western countries. However, estimates of the incidental cases are 5000 per year with a prevalence of 25000 patients (one-third that of the estimate for the United States)(Lad et al., 2018). In India, CLL accounts for 3-5% of all leukaemia types. CLL is a disease of the elderly and the median age of CLL presentation is >60yrs in India. The high-risk CLL is defined, by a genetic aberration of the TP53 gene [i.e., del(17p) or TP53 mutation]. The incidence of high-risk characteristics (del 17p) increase up to 50% in patients with relapsed and refractory CLL (Gogia, Gupta, Kumar, Sharma, & Soni, 2019). An Indian study showed that high-risk cytogenetic abnormalities like del(17p) and del(11q) were seen in 13.3% patients, which are more common in India than that reported in the West. (Saxena, Kumar, Sazawal, & Mahapatra, 2016)

The Scientific Expert Committee (SEC) of Oncology and Haematology, nominated by Central Drugs Standard Control Organisation (CDSCO), met on 12-Feb-2020. The committee provided recommendations to obtain marketing authorization for Acalabrutinib in the treatment of patients with CLL/SLL, and patients with MCL who have received at least one prior therapy. The marketing authorization was provided with a condition to conduct a phase IV clinical trial as per the requirements in the latest New Drug and Clinical Trial Rules (2019) in India. The phase IV trial will be a part of the marketing authorization condition, which will be issued for the additional indication of CLL for Acalabrutinib in India.

In line with the SEC recommendation and to comply with the marketing authorization condition, the current phase IV study plans to assess the safety and efficacy of Acalabrutinib in Indian patients. The data obtained from the study will help to understand the safety and efficacy profile of Acalabrutinib in Indian patients with CLL/SLL, and patients with MCL who have received at

least one prior therapy. The study will add information to currently available safety and efficacy data on Acalabrutinib.

Objectives and Endpoints


Primary objective
 
To investigate the safety of Acalabrutinib among patients with treatment naïve and R/R CLL/ SLL, and relapsed & refractory MCL in Indian patients
	
Outcome measures
 
Adverse Events (AEs), Serious Adverse Events (SAEs), and AEs of Special Interest (AESI) including Arrhythmias (Atrial Fibrillation), Anaemia, Hypertension, Bleeding, Infections, Reasons for discontinuation and second primary malignancies

Secondary objectives
 
To assess the efficacy of Acalabrutinib in patients of CLL/SLL and relapsed & refractory MCL in Indian patients
 
Patient-reported outcome (PRO)
	
Secondary Outcome measures
 
Objective response to treatment.
 
Health related quality of life (EORTC QLQ-C30 Questionnaire)

Overall design

The study is a phase IV, open-label, single-arm, multi-centre, prospective study to be conducted in India. The study will evaluate the safety and efficacy of Acalabrutinib in Indian adult patients with CLL/SLL and patients with MCL who have received at least one prior therapy. The Investigator will be trained on the locally approved Prescribing Information (PI) before the enrolment of the first patient at their site to ensure compliance and proper dosing of the study drug. Patients will be monitored throughout the study period for AEs /SAEs/AESI of Acalabrutinib.

Patients with CLL/SLL and MCL who are eligible to receive Acalabrutinib treatment as per locally approved PI and ratified by an independent clinical judgment of treating physician will be evaluated for inclusion into the current phase IV trial. To enrol approximately 100 patients (90 patients of TN & R/R CLL and 10 R/R MCL patients) into the study, it is expected that approximately 150 patients will need to be screened.

The study will be initiated after approval by the Ethics Committee. Patients will undergo the following phases: Screening/Enrolment Phase, Treatment Phase, and Follow-up Phase.

The decision of patients to participate in this study must not, in any way, impact the standard of care they are receiving or any benefits to which they are otherwise entitled. Prior to data collection, all patients must sign an Informed Consent Form (ICF), allowing for data collection and source data verification to be performed in accordance with local requirements and Sponsor policy.

Two cohorts of patients will be included in the current study (a) patients with CLL/SLL who are treatment naïve or have received at least one prior therapy (N= 90) and (b) patients with MCL

who have received at least one prior therapy (N= 10). Potential patients will undergo screening phase within 07 days prior to the first dose. Patients who meet the protocol-defined inclusion/exclusion criteria will be prospectively enrolled in the study.

Acalabrutinib capsules 100 mg are administered twice daily (BID) for 06 cycles, starting from Cycle 1, Day 1, and continuing up to Cycle 6, Day 28; or until study drug discontinuation due to either disease progression or, unacceptable toxicity, or other reasons, whichever occurs earlier.

Acalabrutinib will be provided by the Sponsor to patients in the Treatment Phase. The Sponsor shall also conduct laboratory investigations for safety and efficacy evaluations, including haematology, biochemistry, radiology, and electrocardiography (ECG), as mentioned in the SoA table.

Patient Population

Inclusion criteria

Patients are eligible to be included in the study only if all of the following inclusion criteria and none of the exclusion criteria apply:

1. Men and Women aged 18yrs or more.
2. Eastern Cooperative Oncology Group (ECOG) performance status of 0,1, or 2
3. Able to receive all outpatient treatments, all laboratory monitoring, and all radiologic evaluations.
4. The following laboratory parameters:
 - a. Absolute neutrophil count (ANC) ≥ 750 cells/ μ L or ≥ 500 cells/ μ L in patients with documented bone marrow involvement, and independent of growth factor support 07 days before the assessment
 - b. Platelet count $\geq 50,000$ cells/ μ L or $\geq 30,000$ cells/ μ L in patients with documented bone marrow involvement, and without transfusion support 07 days before the assessment
 - c. Aspartate transaminase (AST) and Alanine transaminase (ALT) ≤ 2.0 x ULN
 - d. Total bilirubin ≤ 1.5 x ULN
 - e. Estimated creatinine clearance of ≥ 30 mL/min
5. Refractory disease defined as achieving less than partial response with the most recent treatment within 6 months before study entry
6. Provision of signed, written and dated informed consent prior to any study-specific Procedures
7. The patients of either CLL or MCL:
 - a. **CLL patients:**
 - i. Treatment naïve or ≥ 1 prior systemic therapy for CLL
 - ii. Diagnosis of CD20+ CLL that meets published diagnostic criteria (Hallek et al. 2018)
 - iii. An active disease that meets ≥ 1 of the following iwCLL 2018 criteria for requiring treatment:
 - 1) Evidence of progressive marrow failure as manifested by the development of, or worsening of, anaemia and/or thrombocytopenia. Cut-off levels of Hb < 10 g/dL or platelet

counts $<100 \times 10^9/L$ are generally regarded as an indication for treatment. However, in some patients, platelet counts $<100 \times 10^9/L$ may remain stable over a long period; this situation does not automatically require therapeutic intervention.

- 2) Massive (i.e., ≥ 6 cm below the left costal margin) or progressive or symptomatic splenomegaly.
- 3) Massive nodes (i.e., ≥ 10 cm in longest diameter) or progressive or symptomatic lymphadenopathy.
- 4) Progressive lymphocytosis with an increase of $\geq 50\%$ over a 2-month period or Lymphocyte Doubling Time (LDT) in < 6 months. LDT can be obtained by linear regression extrapolation of absolute lymphocyte counts obtained at intervals of 2 weeks over an observation period of 2 to 3 months; patients with initial blood lymphocyte counts $< 30 \times 10^9/L$ may require a longer observation period to determine the LDT. Factors contributing to lymphocytosis other than CLL (e.g., infections, steroid administration) should be excluded.
- 5) Autoimmune complications, including anaemia or thrombocytopenia poorly responsive to corticosteroids.
- 6) Symptomatic or functional extra-nodal involvement (e.g., skin, kidney, lung, spine).
- 7) Disease-related symptoms as defined by any of the following:
 - a) Unintentional weight loss of $\geq 10\%$ within the previous 06 months.
 - b) Significant fatigue (i.e., ECOG performance scale 02 or worse; cannot work or unable to perform usual activities).
 - c) Fever $\geq 100.5^\circ F$ or $38.0^\circ C$ for 02 or more weeks without evidence of infection.
 - d) Night sweats for ≥ 1 month without evidence of infection.

b. MCL Patients:

- i. Confirmed MCL with translocation t(11;14) (q13;q32) and/or overexpressed cyclin D1
- ii. Measurable nodal disease (one or more lesions measuring ≥ 2 cm in the longest diameter)
- iii. Relapsed after, or were refractory to, 1-5 previous treatments

Exclusion criteria

1. Known polymphocytic leukaemia, Central Nervous System (CNS) lymphoma or leukaemia; or known history of (or currently suspected) Richter's syndrome
